### 2.2 Rationale for Study Design

The dose escalation portion of this Phase 1, open-label, dose finding study is designed to establish a safe and tolerated dose of ADCT-502 for further testing in patients with solid tumors expressing HER2 (high and low expressers). Up to nine (9) groups are planned in the expansion portion to further characterize the safety and evaluate preliminary efficacy. As indicated in [Section 4.1](#), the enrollment of the groups is staggered in order to allow for an

evaluation of the therapeutic potential in a limited number of patients with breast and GE cancer prior to exposing patients with other tumor types to ADCT-502.

Part 1 will utilize a modified continual reassessment method (mCRM) to guide dose escalation and estimate the maximum tolerated dose (MTD) and/or determine the recommended dose for expansion (RDE) for ADCT-502. The mCRM and escalation with overdose control (EWOC) enables incorporation of available prior information and updates the model parameters based upon new information about observed dose limiting toxicities (DLT) seen in the clinical study. The dose recommended by the model at any stage of the trial is based on the entire history of all available DLT information from previous cohorts as opposed to only the number of DLTs observed in the last group of patients. Part 2 will utilize the Simon two-stage optimal design with a futility stop and staggered enrollment to minimize exposure of patients when evidence for efficacy is weak.

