### 2.4 Plans and Justification for Provisional Dose Levels

Overall, approximately 10 dose levels are planned. An initial increase of 100% for lower dose levels is foreseen, resulting in provisional dose levels of 30, 60 and 120  $\mu\text{g}/\text{kg}$ . Midstage escalation is somewhat more conservative to account for potential low-grade toxicity to become apparent, with dose level increases of 50%, 33% and 25%, resulting in doses of 180, 240 and 300  $\mu\text{g}/\text{kg}$ . Subsequent levels are determined by a fixed dose increase of 50  $\mu\text{g}/\text{kg}$  (i.e., 300, 350, 400, 450 and 500  $\mu\text{g}/\text{kg}$ ) as the highest dose level to be tested, if allowed by the mCRM with EWOC. The default dosing regimen is once every 3-week dosing. Clinical and pharmacokinetic (PK) data will be reviewed on an ongoing basis and may provide evidence to support interim dose levels. In addition, or as an alternative to decreasing doses to interim dose levels, the dosing interval may be extended (but not shortened), for example, to dosing every 4, 5 or 6 weeks instead of every 3 weeks. Once the dose interval is changed or an intermediate dose not predefined in the mCRM model is used, 3+3 design may be used for future dose escalation. One situation in which such approach may be advantageous is drug accumulation; implementation will need DESC approval (DESC, see [Section 4.6.1](#)) and may affect both ongoing patients as well as new cohorts. Similarly, it is at the discretion of the DESC to modify the dosing regimen that mandates omitting dosing of every n-th cycle, e.g. every 3rd cycle. Note: Scheduled visits will be kept,

except when C2 dosing is skipped; in that case C2D2-D5 would be omitted (respective assessment will not be done). This approach may be beneficial in balancing efficacy and adverse events. The cumulative dose of ADCT-502 in such a revised regimen can only be less than or equal to the cumulative dose of a dose-level that has been tested and found to be safe per mCRM.

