#### **4.6 Description of Dose Escalation Process**

Each cohort will consist of 2 patients. There will be a 24-hour observation before enrolling the second patient at Dose Level 1. The DLT observation period at each dose level is 1 cycle (3 weeks), after which it will be determined whether to escalate to the next dose level, stay at the current dose level, or de-escalate to the previous dose level for the next cohort.

There will be no de-escalation from Dose Level 1. Intrapatient dose escalation is not permitted.

Dose escalation is not permitted unless two or more patients have complete DLT information through the first cycle in any given dose level. Dose escalation will be determined by using a mCRM with a target DLT rate of 30% and an equivalence interval of 20% to 35%, and with dose escalation-with-overdose-control (EWOC) and no dose skipping.

The mCRM will be implemented in Part 1 under the oversight of a Dose Escalation Steering Committee (DESC). The DESC will confirm each escalating dose level after reviewing all available safety data. PK data from patients in that dose level and prior dose levels may also inform decision making. The DESC may halt dose escalation prior to determining the MTD based on emerging PK, PD, toxicity, or response data.

Additional patients may be included at any dose level to further assess the safety and tolerability if at least 1 patient in the study has achieved a partial response or better, or if further evaluation of PK or PD data is deemed necessary by the DESC to determine the RDE.

Furthermore, to better understand the potential efficacy of ADCT-502 in an indication approved for treatment with HER2 targeted antibodies, up to 3 additional breast cancer patients who have previously been treated with an approved HER2 targeted therapy may be enrolled per cohort at given dose levels  $\geq 60 \mu\text{g/kg}$  determined by the mCRM model to be safe.

Dose escalation will be stopped after the mCRM has assigned 3 cohorts consecutively to the same dose level.

If the MTD is not reached, the recommended dose(s) and schedule(s) for expansion (RDE) will be determined.

Once the Part 2 RDE(s) is/are determined, patients receiving lower or higher dose levels of ADCT-502 enrolled in part 1 may be offered continued treatment at the RDE(s).

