### 18.4.3 Dose Escalation Rule and Choice of Cohort Size

Dose escalation will begin with 2 patients enrolled at the initial starting dose. The cohort size is 2, which means that 2 patients will be assigned to escalate to the next dose level, de-escalate to the prior dose level, or, stay at the current dose level.

On the completion of each cohort (i.e., 2 patients treated and assessed for DLT after 1-cycle), the posterior distributions of  $\theta(d)$  are summarized for each dose level by the probabilities of under-dosing, targeted toxicity, or excessive/unacceptable toxicity. These 3 probabilities are defined as:

$$\text{Under-dosing: } \theta_d \in (0, 0.20)$$

$$\text{Targeted Toxicity: } \theta_d \in [0.20, 0.35]$$

$$\text{Excessive or Unacceptable Toxicity: } \theta_d \in (0.35, 1]$$

The dose which maximizes the probability of targeted toxicity while controlling the probability of excessive or unacceptable toxicity to  $\leq 25\%$  will be recommended for the next cohort of 2 patients. The model has the flexibility for a larger cohort size if additional patient are available.

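### After one response anywhere in the study, patients may be added at any dose level, including tested levels that the mCRM has since judged too toxic

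*Protocol*

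**What the plan says.** Section 4.6, repeated in the synopsis under the Part 1 design, gives two triggers for enrolling beyond the model cohorts. The first is a response: "Additional patients may be included at any dose level to further assess the safety and tolerability if at least 1 patient in the study" has a partial response or better. The second is "or if further evaluation of PK or PD data is deemed necessary by the DESC to determine the RDE". The committee's judgement is written into the second trigger only. The response need not have occurred at the level being enlarged, and there is no cap on numbers.

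Elsewhere the protocol does tie enrolment or dosing to the model:

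- **Section 4.6, next paragraph.** Up to 3 extra breast cancer patients per cohort may enter at levels of 60 µg/kg or more, provided the level is "determined by the mCRM model to be safe".
- **Section 2.4.** The cumulative dose of a revised regimen may not exceed that of "a dose-level that has been tested and found to be safe per mCRM".
- **Section 18.4.3.** The dose that maximises the probability of targeted toxicity, with the probability of excessive toxicity (DLT rate above 0.35) held to 25% or less, "will be recommended for the next cohort of 2 patients".

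**The concern.** The permission covers every dose level and carries no safety condition, while the adjacent paragraph has one. A reader comparing the two could take the omission as intended. The exposed levels are those already tested and later rejected by the model. Untested levels are still protected by the no-skipping rule and by DESC confirmation of each escalation step.

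At stake is patient exposure in a first-in-human study. As written, patients could be added at a dose whose current probability of excessive toxicity is above the design's own 25% limit.

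**Working it through.** The documents give no figure for this enrolment, so there is none to reproduce. The check has two parts: whether any other text closes a rejected level, and whether such levels can arise.

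**1. Other text that might close the gap**

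| Place | What it governs | Closes a rejected tested level? |
|---|---|---|
| 18.4.3, 25% limit | Dose for the next cohort of 2 | Not stated for additional patients |
| 18.4.3, larger cohorts | Cohort size | No; silent on which levels stay open |
| 4.6, DESC confirmation | Each escalating dose level | No; returning to a tested level is not escalation |
| 4.6.1, ongoing DESC review | Whether the escalation schedule needs changing | Discretionary, no threshold |
| 18.4.4.1, safety stop | Lowest dose only | No |
| SAP 4.8.1 | DLT data listed | No |

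The 18.4.4.1 stop is no backstop. The prior in 18.4.2 bounds the DLT probability at the starting dose at 0.30, so the probability that it exceeds 0.35 there is always 0.

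**2. Posterior probabilities under the protocol's model**

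Inputs:

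- Section 18.4.2: two-parameter logistic model, ρ₀ ~ U(0, 0.30) at d₁ = 30 µg/kg, and γ (the dose with DLT probability 0.30) ~ U(d₁, dₙ).
- Table 9: dₙ = 500 µg/kg, so γ ~ U(30, 500).
- Section 18.4.3: level rejected if P(DLT rate > 0.35) > 0.25.

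The model line in 18.4.2 uses log dose, but the printed formula for γ is linear in dose, so both scales were run on a 1500 × 1500 grid:

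logit p(d) = logit ρ₀ + [logit 0.30 − logit ρ₀] × f(d)

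Here f(d) = log(d/30)/log(γ/30) on the log scale, or (d − 30)/(γ − 30) on the linear scale.

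| Data (DLTs/patients) | Level (µg/kg) | P(DLT rate > 0.35), log | Linear |
|---|---|---|---|
| 0/2 at 30, 0/2 at 60, 2/2 at 120 | 60 | 0.101 | 0.114 |
| same | 120 | 0.368 | 0.558 |
| plus a further 0/2 at 60 | 120 | 0.317 | 0.525 |
| 0/2 at 30, 60 and 120; 2/2 at 150 | 150 | 0.230 | 0.363 |

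In the first case 120 µg/kg fails the 25% limit, 60 µg/kg passes, and the model moves down to 60. The posterior mean DLT rate at 120 is then 0.40 (log) or 0.53 (linear), against a 30% target. Two further DLT-free patients at 60 do not bring 120 back under the limit. Section 4.6 would still allow patients to be added at 120 if anyone in the study had responded.

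**3. How often a rejected tested level exists**

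The simulation used 2000 runs per protocol scenario. Assumptions: cohorts of 2, at most 30 patients, one-level escalation steps, stop after 3 consecutive cohorts at one level or if level 1 is unsafe, and no additional patients.

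| Scenario (18.4.5.1) | Tested level ever above 25%, log | Linear |
|---|---|---|
| 1 | 0.739 | 0.873 |
| 2 | 0.234 | 0.722 |
| 3 | 0.037 | 0.409 |
| 4 | 0.304 | 0.699 |
| 5 | 0.170 | 0.505 |

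The worked path itself is uncommon. From the scenario DLT rates, its probability is:

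- Scenario 1: 0.90² × 0.83² × 0.30² = 0.050
- Scenario 4: 0.90² × 0.875² × 0.16² = 0.016
- Scenario 3: 0.98² × 0.96² × 0.06² = 0.003

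The simulated shares are larger because many other paths also lead to a rejected level.

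**The case against.** The strongest reply is that the DESC would not allow it. Section 4.6 puts Part 1 under its oversight, 4.6.1 has it review safety continually, and the sentence says only that patients may be added. The sponsor and investigators would have to choose a dose they had just left. That is a fair prediction of conduct, and it limits the practical hazard. It is not a written limit, and the same committee oversees the breast cancer enrolment, where the limit was written in.

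A second reply is that additional patients could be read as enlarging a model-assigned cohort, since 18.4.3 allows larger cohorts, so that the 25% limit already applies. That reading is possible, but 18.4.3 does not say so, and the words in 4.6 about any dose level point the other way.

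Third, the comparators differ in purpose. Section 2.4 concerns revised schedules and is the looser parallel. The breast cancer paragraph serves efficacy, while this rule serves safety, tolerability and PK/PD. That does not explain why a safety-motivated enrolment should carry the weaker safety condition.

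Fourth, the figures can be read as too large. The highest come from the linear scale, which conflicts with the stated model line. The shares also count levels above 25% only for a time. In a smaller rerun (250 runs per scenario), the share with such a level at the end of escalation was 59% (log) or 81% (linear) in scenario 1, 19% or 49% in scenario 4, and 2% or 13% in scenario 3. None of the shares includes the response trigger or a decision to enrol. All of this stands as a limit on what the figures show. It does not remove the gap.

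**Conclusion.** The concern holds. The response trigger has no model-safety condition and no written committee decision, and no other text closes a tested level that the model has since rejected. The protocol's own priors produce such levels: 120 µg/kg stands at 0.37 (log) or 0.56 (linear) after 2/2 DLTs there, against a limit of 0.25. Across the five scenarios, a rejected tested level exists at some point in 4% to 74% of runs on the log scale and 41% to 87% on the linear scale.

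Confidence is high for the missing condition. The posterior figures rest on the assumed DLT counts and the dose scale, and the simulated shares also on the listed escalation assumptions. They show that the situation can arise, not how often patients would be exposed. The change should be made: it is a cheap improvement that affects no endpoint, analysis or sample-size rule.

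**What to change.** In section 4.6 and the synopsis, state that additional patients under either trigger may be enrolled only at already tested dose levels that the current mCRM finds safe, meaning P(DLT rate > 0.35) of 25% or less on current data, and only with DESC approval.

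Section 2.2 already makes the model's recommendation "based on the entire history of all available DLT information from previous cohorts", so only the timing needs adding: available DLT data from these patients enter the model before the next dose decision.

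The cost is one clause in two places and the loss of freedom to add patients at levels the model has rejected. The clause does not close every level with DLTs. After 2/2 at 150 µg/kg following three DLT-free cohorts, that level stays open on the log scale (0.23) and closes on the linear scale (0.36). DESC judgement would still be needed there.

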**Part 2 (Dose Expansion):**

HER2-high\* or HER2-low\*\* advanced solid tumor belonging to one of the pre-specified indications for groups A – E (breast cancer, gastric & gastroesophageal cancer, bladder cancer, non-small cell lung cancer) or one of the eight pre-specified indications for the basket group

(SCLC, CRC, pancreatic, biliary tract, prostate, ovarian, endometrial, or salivary gland) according to assigned treatment group for which HER2 status has been confirmed prospectively (HER2-high or HER2-low) for study entry.

\* A HER2-high patient is defined as IHC 3+, or IHC 2+ with FISH amplification.

\*\* A HER2-low patient is defined as IHC 1+, or IHC 2+ without FISH amplification.

Note: A patient with IHC 0 / IHC 1+ with amplification is HER2-high for study purposes; a patient with IHC 3+ with negative amplification results is HER2-low for study purposes.

6. Part 2/Dose Expansion Only: Measurable disease as defined by Response Evaluation Criteria in Solid Tumors (RECIST) version 1.1.

Note: Lytic bone lesions or mixed lytic-blastic lesions, with identifiable soft tissue components, that can be evaluated by cross sectional imaging techniques such as CT or MRI can be considered as measurable lesions if the soft tissue component meets the definition of measurability per RECIST.

7. Screening laboratory values within the following parameters:

- a. Absolute neutrophil count (ANC)  $\geq 1500/\text{mm}^3$  ( $\geq 1.5 \times 10^9/\text{L}$ ).
- b. Platelet count  $\geq 100,000/\text{mm}^3$  ( $\geq 100 \times 10^9/\text{L}$ ).
- c. Hemoglobin  $\geq 9 \text{ g/L}$  ( $\geq 5.6 \text{ mmol/L}$ ).
- d. Aspartate transaminase (AST) and alanine aminotransferase (ALT)  $\leq 2.5 \times$  upper limit of normal (ULN); or  $\leq 5.0 \times$  ULN if liver metastases are present.
- e. Total bilirubin  $\leq 1.5 \times$  ULN (or  $\leq 3 \times$  ULN, with direct bilirubin  $\leq 1.5 \times$  ULN, in patients with known Gilbert syndrome).
- f. Serum/plasma creatinine  $\leq 1.5 \times$  ULN; or, if creatinine  $> 1.5 \times$  ULN, a measured creatinine clearance must be  $> 60 \text{ mL/min}$  as calculated by the Cockcroft and Gault equation for patient to be eligible.

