#### **Part 1 (Dose Escalation):**

Advanced solid tumors with documented HER2 status of IHC  $\geq 1+$  or HER2

amplified/mutated by FISH or NGS (refer to [Section 4.2](#) and [Appendix 18.3](#)).

**Note:** Clinical pathology report of HER2 status must be available for review to confirm eligibility in Part 1.

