**Part 2 (Dose Expansion):**

HER2-high\* or HER2-low\*\* advanced solid tumor belonging to one of the pre-specified indications for groups A – E (breast cancer, gastric & gastroesophageal cancer, bladder cancer, non-small cell lung cancer) or one of the eight pre-specified indications for the basket group (SCLC, CRC, pancreatic, biliary tract, prostate, ovarian, endometrial, or salivary gland) according to assigned treatment group for which HER2 status has been confirmed prospectively (HER2-high or HER2-low) for study entry.

\* A HER2-high patient is defined as IHC 3+, or IHC 2+ with FISH amplification.

\*\* A HER2-low patient is defined as IHC 1+, or IHC 2+ without FISH amplification.

Note: A patient with IHC 0 / IHC 1+ with amplification is HER2-high for study purposes; a patient with IHC 3+ with negative amplification results is HER2-low for study purposes.

6. **Part 2/Dose Expansion Only:** Measurable disease as defined by Response Evaluation Criteria in Solid Tumors (RECIST) version 1.1.

Note: Lytic bone lesions or mixed lytic-blastic lesions, with identifiable soft tissue components, that can be evaluated by cross sectional imaging techniques such as CT or MRI can be considered as measurable lesions if the soft tissue component meets the definition of measurability per RECIST.

7. Screening laboratory values within the following parameters:
  - a. Absolute neutrophil count (ANC)  $\geq 1500/\text{mm}^3$  ( $\geq 1.5 \times 10^9/\text{L}$ ).
  - b. Platelet count  $\geq 100,000/\text{mm}^3$  ( $\geq 100 \times 10^9/\text{L}$ ).
  - c. Hemoglobin  $\geq 9 \text{ g/L}$  ( $\geq 5.6 \text{ mmol/L}$ ).
  - d. Aspartate transaminase (AST) and alanine aminotransferase (ALT)  $\leq 2.5 \times$  upper limit of normal (ULN); or  $\leq 5.0 \times$  ULN if liver metastases are present.
  - e. Total bilirubin  $\leq 1.5 \times$  ULN (or  $\leq 3 \times$  ULN, with direct bilirubin  $\leq 1.5 \times$  ULN, in patients with known Gilbert syndrome).
  - f. Serum/plasma creatinine  $\leq 1.5 \times$  ULN; or, if creatinine  $> 1.5 \times$  ULN, a measured creatinine clearance must be  $> 60 \text{ mL/min}$  as calculated by the Cockcroft and Gault equation for patient to be eligible.

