## **10.3 Efficacy Assessments**

Computerized tomography (CT) or magnetic resonance imaging (MRI) scans with contrast of the chest, abdominal and pelvic area or brain scans (CT or MRI with contrast), and bone scans or X-ray exam if clinically indicated, will be performed. For image acquisition specifications, including instruction in the event of allergy to contrast dye, refer to Appendix II of RECIST version 1.1 (Specifications for Standard Anatomical Radiological Imaging).

The same methods used at baseline that identify sites of disease should be used uniformly for all subsequent assessments. Response to treatment will be determined by the Investigator as complete response (CR), partial response (PR), stable disease (SD), or progressive disease (PD) according to RECIST version 1.1.

Images will be obtained according to local site imaging requirements and may be required to be submitted for a central/independent review. Submission instructions for the central/independent review will be provided in a separate manual.

Once the final efficacy analysis for progression-free survival (PFS) is performed (Part 2), the frequency of tumor response assessment for patients remaining under treatment may be further decreased and/or performed according to standard of care.

[REDACTED]

[REDACTED]

[REDACTED]

[REDACTED]

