### **12.5.1 Overall Response Rate**

ORR will be defined as the proportion of patients with a best overall response of CR or PR at the time each patient discontinues ADCT-502. The percentage of ORR with its 80% confidence interval (CI) will be presented.

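### The optional Part 1 breast cancer patients added for efficacy need not have measurable disease, so some may be unable to show a partial response

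*Protocol*

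**What the plan says.** Protocol Section 4.6, repeated in the synopsis, gives one purpose for the extra patients: "to better understand the potential efficacy of ADCT-502 in an indication approved for treatment with HER2 targeted antibodies, up to 3 additional breast cancer" patients may be added to a cohort. The condition placed on them is prior treatment: "patients who have previously been treated with an approved HER2 targeted therapy may be enrolled per cohort at given dose levels" of 60 µg/kg or more that the model has found safe. Measurability is not mentioned.

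The disease criterion for Part 1 (criterion 5, synopsis and Section 6.1) concerns HER2 status only: "Advanced solid tumors with documented HER2 status of IHC" 1+ or higher, or amplification or mutation. Criterion 6 reads "Part 2/Dose Expansion Only: Measurable disease as defined by Response Evaluation Criteria in Solid Tumors (RECIST) version 1.1". Its note says that lytic or mixed bone lesions with a soft tissue component "can be considered as measurable lesions if the soft tissue component meets the definition of measurability per RECIST".

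Section 10.3 has the investigator assess response by RECIST 1.1. Section 12.5.1 states that "ORR will be defined as the proportion of patients with a best overall response of CR or PR". The Efficacy Population in Section 12.3 asks for a valid baseline assessment and at least one valid post-baseline assessment, with an exception for documented progression and death. It does not ask for measurable disease.

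SAP Section 4.9 limits efficacy output to listings, including target, non-target and new lesions, because the trial stopped early.

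**The concern.** Leaving measurability out of Part 1 is reasonable for patients enrolled to find a dose. Section 4.2 uses the same logic when it justifies looser HER2 testing in Part 1 by the different goals of the two parts. That logic does not carry over to patients who are added to a dose-escalation cohort for an efficacy question. The summary of changes for Amendment 2, which introduced this group, lists revisions to inclusion criteria 4, 5 and 7 but none to criterion 6. That fits an oversight but does not prove one.

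The protocol expects bone disease. It provides for bone scans (Section 10.3), radiotherapy to lytic lesions (Section 9.3.1) and bisphosphonates or denosumab (Section 9.3.8). A patient with bone disease alone and no qualifying soft tissue component could therefore enter the added group.

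Two things are at stake. Some of the extra exposure may not yield the response information that is its stated reason. Part 1 responses can also influence conduct: under Section 4.6, one partial response or better permits additional patients at any dose level, and the steering committee may halt escalation on response data, among other grounds.

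**Working it through.** **1. Text.** Four places could require measurable disease of the added patients.

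| Place | Requires measurable disease? |
|---|---|
| Section 4.6 and synopsis, conditions on the added group | No |
| Criterion 5, Part 1 | No, HER2 status only |
| Criterion 6 | Yes, but Part 2 only |
| Section 12.3, Efficacy Population | No |

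Two steps rest on inference. First, RECIST 1.1 bases a partial response on shrinkage of measurable target lesions; the protocol adopts those criteria without reproducing them. Second, Section 12.5.1 names no denominator, and Section 12.3 does not define a valid baseline assessment. That a patient with only non-measurable disease would count in the ORR denominator is the natural reading, but it is not spelled out.

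**2. Size.** The plan states no figure for this group, so there is none to reproduce. The inputs are:
- n = 3 added patients in one cohort (Section 4.6).
- p = 25% response in patients with measurable disease. This is borrowed from the Part 2 alternative in Section 12.1; no rate is given for Part 1.
- f = share without measurable disease. The documents give none; 10-30% is assumed.
- No response of any kind is counted in patients without measurable disease. This is a worst case, because a complete response remains possible.

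The chance of response per added patient is p(1 − f). The chance of at least one response among three is 1 − [1 − p(1 − f)]³. The chance that at least one of the three lacks measurable disease is 1 − (1 − f)³.

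| f | p(1 − f) | At least one response in 3 | At least one of 3 not measurable |
|---|---|---|---|
| 0 | 0.250 | 1 − 0.750³ = 58% | 0% |
| 10% | 0.225 | 1 − 0.775³ = 53% | 1 − 0.9³ = 27% |
| 20% | 0.200 | 1 − 0.800³ = 49% | 1 − 0.8³ = 49% |
| 30% | 0.175 | 1 − 0.825³ = 44% | 1 − 0.7³ = 66% |

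Requiring measurable disease sets f to 0 and restores the first row.

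**3. How many added patients there could be.** Section 4.3 estimates approximately 30 patients for all of Part 1. Assume that this includes the added patients and that dose level 1 uses one cohort of 2. With k cohorts of 2 at 60 µg/kg or above, the number of added patients is at most the smaller of 3k and 30 − 2 − 2k.
- k = 5: smaller of 15 and 18 = 15
- k = 6: smaller of 18 and 16 = 16
- k = 7: smaller of 21 and 14 = 14
- k = 10: smaller of 30 and 8 = 8

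The maximum is about 16 on any path, and about 8 on a ten-cohort path.

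**The case against.** The best reply is that efficacy in this protocol is wider than partial response. Sections 3.2.2 and 12.5 define it through ORR, disease control, duration of response, PFS and OS. Progression, death and complete response can all be assessed without a target lesion. The added patients also receive study drug in Part 1, so they fall within the Safety and DLT Evaluable definitions (the latter unless they stop in Cycle 1 without a DLT) and contribute PK samples. A reader might infer that a patient without measurable disease is exposed for nothing; the documents do not support that. The loss concerns partial response, and hence ORR.

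The effect on conduct is also limited. The trigger in Section 4.6 can be met by any patient in the study, by a complete response as well as a partial one, and has PK or PD need as an alternative. Part 2 futility decisions rest on Part 2 patients, to whom criterion 6 applies.

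Finally, the SAP plans no ORR. A reader might infer that a reported Part 1 response rate is biased downwards, but SAP Section 4.9 lists efficacy data only and SAP Section 4 rules out hypothesis testing. Because target and non-target lesions are both listed, a missing target lesion can be found patient by patient.

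All of this stands and keeps the severity low. It does not close the eligibility gap: a group added for efficacy lacks the entry condition that Part 2 applies to its own patients.

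**Conclusion.** The point holds as a modest inconsistency between the stated purpose of the added group and its entry criteria. Some of these patients may be unable to show a partial response; the documents do not establish that any will be.

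Under the worst-case assumptions above, the chance of seeing at least one response among three added patients drops by about 4 to 14 percentage points (57.8% to 53.5% at f = 10%, and to 43.8% at f = 30%). The result depends on the assumed share, on a 25% rate borrowed from the expansion dose, and on counting no complete responses in patients without measurable disease.

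A reader might also multiply three patients by a long run of cohorts and conclude that many are affected. Ten cohorts filled in this way would give 2 + 20 + 30 = 52 patients, well above the approximately 30 estimated for Part 1. Enrollment of the group is also optional, so the per-cohort figures are the safer basis.

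No stated sample size, type I error or power is affected. Rating: cheap improvement, low severity.

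**What to change.** In Section 6.1 and the synopsis, change the scope of criterion 6 to: *Part 2, and the additional breast cancer patients enrolled for efficacy under Section 4.6*. The other Part 1 patients need no change.

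If any Part 1 ORR is presented, give it among patients with measurable disease at baseline and state how many lack it.

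In the efficacy listing of SAP Section 4.9, add a flag for measurable disease at baseline. With the trial stopped, this is the part that still applies to the existing data. The eligibility change matters if the protocol text is reused.

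The cost is one line in two places, one listing column, and slightly slower accrual of an optional group.
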